4. SUBJECT POPULATIONS

The Intent-To-Treat (ITT) population, the Per Protocol (PP) population and the PK population are mentioned in the protocol but will not be identified in the final analyses due to the early termination of the study and the limited amount of data.

4.1 Randomized Population

The randomized population consists of all subjects who are randomized at Visit 2 to one of the five treatment groups: JTE-051 50 mg QD, 100 mg QD, 150 mg QD, 200 mg QD and placebo QD.

4.2 Safety Population

The safety population consists of the randomized subjects who receive at least one dose of JTE-051 or placebo after the randomization, including those who did not complete the study.

5. STATISTICAL ANALYSIS

The study was terminated early due to the results of another study on the same compound and slow enrollment in this study. Therefore, the planned sample size of 85 eligible subjects (17 in each treatment group) was not achieved. With only 13 subjects randomized until the early study termination, there will not be enough data to analyze the planned efficacy and safety endpoints. No inferential tests will be performed. Most of the data will be displayed in listings only.

Titles and headers of all statistical analysis tables will indicate the corresponding study population; the number of subjects for the population and for each treatment will be presented in the tables.

Percentages will be presented to 1 decimal, e.g., xx.x%.

Baseline is defined as the last non-missing value prior to the first dose of study drug. Missing data will not be imputed in this study.

Unless otherwise noted, all records collected in the study database, including CRF data and any external data transfers (such as clinical laboratory results) will be displayed in listings, regardless of whether the subject is randomized or not.

All analysis will be performed using SAS® Version 9.4.

5.1 Disposition

Subject disposition will be summarized and tabulated by treatment group and in total. The number and percentage of subjects in the randomized and safety populations will be tabulated. Number of discontinued subjects and the reasons for discontinuation during the double-blind (DB) treatment period will be tabulated for the randomized population.

5.2 Safety

The Medical Dictionary for Regulatory Activities (MedDRA) Version 21.0 will be used to map verbatim AEs to preferred terms and their respective primary system organ classes.

A treatment-emergent AE (TEAE) is defined as any AE with an onset date on or after the first dose of study drug.

The number and percentage of subjects experiencing TEAEs will be tabulated by treatment in an overall summary as well as by preferred term and system organ class for the safety population. Listings will be provided for serious adverse events (SAEs) and AEs leading to study discontinuation.

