ITT	Intent-to-treat population
IV	Intravenous
IWRS	Interactive Web Response System
LC-MS/MS	Liquid chromatography/tandem mass spectrometry
LCL	Lower confidence level
LDH	Lactate dehydrogenase
LOCF	Last observation carried forward
LRV	Lower reference value
MedDRA	Medical Dictionary for Regulatory Activities
MOA	Mechanism of action
mRNA	Messenger ribonucleic acid
MTD	Maximum tolerated dose
MTX	Methotrexate
N/A	Not applicable
NOAEL	No observed adverse effect level
NSAID	Non-steroidal anti-inflammatory drug

[figure not shown]
Abbreviation	Definition of term
OAT	Organic anion transporter
OATP	Organic anion transporting polypeptide
OCT	Organic cation transporter
OECD	Organization for Economic Co-operation and Development
PASI	Psoriasis area and severity index
P-gp	P-glycoprotein
pH	Logarithmic measure of hydrogen ion concentration
PI	Principal Investigator
PK	Pharmacokinetic(s)
PP	Per protocol
PR	Interval from beginning of the P wave to the beginning of the QRS complex in the frontal plane
PT	Prothrombin time
QD	Once daily
QOL	Quality of life
QTcF	Fridericia-corrected QT Interval
RA	Rheumatoid arthritis
RR	Interval from beginning of the QRS complex in the frontal plane to the next QRS complex
SAE	Serious adverse event(s)
SAP	Statistical analysis plan
SAS	Statistical analysis system
SD	Standard deviation
Skindex-16	A 16-item, skin-related quality of life questionnaire
SOC	System organ class(es)
SPF	Sun protection factor
sPGA	Static Physician's Global Assessment
SUSAR	Suspected unexpected serious adverse reaction
TB	Tubercle bacillus
TCR	T cell receptor
TEAE	Treatment-emergent adverse event
TG	Triglycerides
TNSn	Total neuropathy score nurse
Treg	Regulatory T cells
TSH	Thyroid stimulating hormone
TV	Target value
UCL	Upper confidence level
WI-NRS	Worst-Itch Numeric Rating Scale

Protocol Synopsis

STUDY TITLE	A Multicenter, Randomized, Double-blind, PlaCebo-controlled, Parallel-group Study to EvaLuate the Safety and Efficacy of JTE-051 Administered for 12 Weeks in Subjects with ModeRate to Severe Plaque PSoriasis (CLEAR-PS)
PROTOCOL NUMBER	AE051-G-16-007
CLINICAL PHASE	Phase 2a
STUDY DURATION	Approximately 20 weeks duration per subject: 
• Up to 28-day Screening Period• 12-week double-blind Treatment Period• 4-week Follow-up Period

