 - j. Subjects will be instructed to bring all used and unused blister cards to each study visit for accountability purposes. Study drug compliance will be calculated by the site at each visit during the Treatment Period starting at Visit 3, based on the number of tablets dispensed to and returned by the subject.
 - k. Oral administration for 12 weeks starting on the day of randomization at Visit 2, QD in the morning, regardless of meals. On study visit days, subjects should take their scheduled study treatment from their existing study drug supply (if available) at the site, under the supervision of the investigator or designee after all study-related procedures have been performed (except for Visit 6, when no study drug will be administered, as the last dose will be taken the day prior to the visit).
 - l. See [Figure 2](#) for a detailed description of dosing and PK sampling time points.
 - m. Adverse event information will be collected at the specified time points as well as at any time when a site staff member becomes aware of an AE after the subject signs the informed consent for the study. However, stable or improving pre-existing conditions detected through the screening procedures during the Screening Period (e.g., abnormalities in ECG, physical examination, [REDACTED] vital signs and laboratory tests) are considered to be medical history and should be documented accordingly.

[figure not shown]

Figure 2. Dosing and Pharmacokinetic Sample Collection Time

- The exact date and time of dose at each visit at the site will be collected.
- The exact date and time of the last three doses prior to the PK sample collection will be collected.
- The PK samples at pre-dose point (i.e., samples obtained prior to the morning dosing of the study drug at the site) are mandatory in all subjects at all sites. Sample collection date and time will be collected.
- The PK samples at trough point (relative to dosing of the study drug at the day prior to the visit) are mandatory in all subjects at all sites. Sample collection date and time will be collected.
- Every effort should be made to collect post-dose PK samples (relative to the morning dosing of the study drug at the site) from as many subjects/treatment as possible. Sample collection date and time will be collected.
- The sampling time between post dose blocks (boxes in Figure 2) should be separated by at least 1 hour.

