3.6.3 Reporting Adverse Events

Adverse Events Reporting

Adverse events occurring (initial occurrence or a worsening of a pre-existing condition) after the informed consent has been signed and up to 4 weeks (28 days) after the last dose of study drug will be reported and included in the study database. However, pre-existing conditions detected as part of the screening procedures should be documented as medical history. Worsening of the underlying condition (i.e., plaque psoriasis) or signs/symptoms associated with this condition should not be reported as an AE unless they meet at least one serious criterion; in such case when they would be reported as both an AE and an SAE. Adverse events will be reported on the AE CRF page.

Serious Adverse Event Reporting

Reporting by Investigators

Detailed instruction regarding SAE reporting will be provided in the appropriate documents outside of this protocol. A brief, non-all-inclusive summary is provided below.

Any SAE experienced by a study subject after signing the informed consent up to 28 days after the last dose of study drug will be reported to the Sponsor or designee. Additionally, SAEs that occur after this period will also be reported to the Sponsor or designee if the Investigator considers the SAE possibly related or related to the study drug.

Serious adverse events (both initial reports and follow-up information) must be reported to the Sponsor or designee within 24 hours of the Investigator's (site's) awareness or notification of the event.

The Investigators should make every effort to provide complete information when reporting the SAE (both for initial reports, as well as for follow-ups).

The Investigator must continue to follow the subject until the SAE has subsided, the condition becomes chronic in nature, stabilizes (in the case of persistent impairment), or the subject dies. Within 24 hours of receipt of follow-up information, the Investigator must submit it to the Sponsor or designee.

The Investigator is also required to submit SAE reports to the IRB/IEC in accordance with local requirements. All investigators involved in studies using the same IMP will receive any Suspected Unexpected Serious Adverse Reaction (SUSAR) reports for onward submission to their local IRB/IEC as required. All reports sent to investigators will be blinded.

Reporting by the Sponsor

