1. INTRODUCTION

This Statistical Analysis Plan (SAP) describes the statistical methods and data presentations to be used in the summary tables and listings of study AE051-G-16-007. No figures are planned due to the limited amount of data.

This document has been prepared based on Protocol Amendment 4, Version 5.2 – 8 Oct 2018 and Case Report Form (CRF) Amendment 1, Version 2.0 – 22 May 2018. Details on the study conduct and data collection can be found in the protocol and the CRF.

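### Does defining a TEAE by onset date alone lose adverse events that worsen after the first dose?

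*SAP*

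**What the plan says.** The SAP's rule is in section 5.2: "A treatment-emergent AE (TEAE) is defined as any AE with an onset date on or after the first dose of study drug". It governs Tables 14.3.1.1 and 14.3.1.2, which count subjects with TEAEs by treatment. The protocol does not compete with it. Its abbreviation list spells out the term as "Treatment-emergent adverse event" and goes no further, and Protocol 3.8.4.2 gives no rule.

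Collection and recording are set by the protocol:

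- Section 3.6.3 puts these in the database: "Adverse events occurring (initial occurrence or a worsening of a pre-existing condition) after the informed consent has been signed and up to 4 weeks" after the last dose.
- The same section removes most changes in the disease under study: "Worsening of the underlying condition (i.e., plaque psoriasis) or signs/symptoms associated with this condition should not be reported as an AE unless they" meet a seriousness criterion.
- Note m to the schedule of procedures (Protocol 3.5, repeated in SAP 3.1) limits what goes to medical history: "However, stable or improving pre-existing conditions detected through the screening procedures during the Screening Period".

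For anything finer, SAP 1 points elsewhere: "Details on the study conduct and data collection can be found in the protocol and the CRF". On reporting, SAP 5 says "Unless otherwise noted, all records collected in the study database, including CRF data and any external data transfers (such as clinical laboratory results) will" be listed, whether or not the subject was randomized.

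**The concern.** Adverse events are collected from consent, so some can begin before any study drug is taken. That window can be long. Screening lasts up to 28 days, Protocol 3.5.1 lets washout start at consent independently of those 28 days, and Protocol Table 2 sets a washout of at least 12 weeks for biologics. An event that starts in this window, is still present on Day 1 and becomes more severe on treatment is one a safety reader would want counted. Read literally, an onset-date rule leaves it out if the record keeps its pre-dose date.

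The omission would fall on tables that matter here. After early termination, subject disposition and the two TEAE tables are the only summary counts left in SAP 6.1. Almost everything else is listed only. An undercount would understate on-treatment harm in the one place where harm is summarized.

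**Working it through.** There is no figure in the plan to reproduce, so the check is to sort the possible cases and see which of them the SAP rule misses.

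**Step 1. Sort by when the problem began and what happened next.**

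| Case | How the protocol treats it | Under SAP 5.2 |
|---|---|---|
| New event on or after first dose | Adverse event, post-dose onset | Counted |
| Medical-history condition that first worsens after first dose | Worsening is itself an adverse event (3.6.3), normally with a post-dose onset | Counted |
| Psoriasis worsens, not serious | Not an adverse event (3.6.3) | Outside the question |
| Psoriasis worsens and is serious, after first dose | Adverse event and SAE, normally with a post-dose onset | Counted |
| Event starts between consent and first dose and does not worsen after dosing | Adverse event, pre-dose onset | Left out, as it should be |
| Event starts between consent and first dose, is open at dosing, then worsens | Depends on how the worsening is recorded | Open |

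Only the last row is in doubt. It is a loss only if four things hold together: the event begins after consent and before dosing; it is still open at the first dose; it then increases in severity or becomes serious; and it keeps its original onset date.

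**Step 2. Ask how the protocol would have the last row recorded.** Neither document states this outright, but three places bear on it.

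- Protocol 3.6.3 treats worsening as an occurrence in its own right, alongside first occurrence.
- Protocol 3.6.1, in its hospitalization definition, says that no adverse event is present where a pre-existing condition has not worsened since consent. The implication is that worsening creates one.
- Protocol 3.6.2 ties the action-taken categories to treatment status when the event occurred. An event before the first dose is coded as not applicable. The interrupted and withdrawn categories require the subject to have been on treatment. A worsening that led to interruption or withdrawal therefore fits the form only as a separate event.

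**Step 3. Follow both branches.**

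- *Worsening entered as a new record.* Its onset is after the first dose, SAP 5.2 counts it, and an added worsening clause changes no count.
- *Worsening kept in the original record.* Protocol 3.6.2 describes one severity assessment per event (mild, moderate or severe). A single grade does not show whether severity rose after dosing. A worsening clause in the SAP would then have little to act on, and the practical fallback would be to flag pre-dose events still open at first dose. Those records are already in Listing 16.2.7.

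**Step 4. Ask what could be lost.** SAP 5 states that 13 subjects were randomized, that no inferential tests will be done, and that most data will be shown in listings only. Every adverse event record appears in Listing 16.2.7. A serious event also falls under Listing 14.3.2.1, whose title is not restricted to TEAEs. No percentage effect can usefully be given. Disposition is planned with a total ("Subject disposition will be summarized and tabulated by treatment group and in total"), but SAP 5.2 plans the TEAE tables by treatment and mentions no total. Arm sizes are not stated, and nothing in the documents suggests how often the last row would occur.

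**The case for a change.** The best case for a change is that SAP 5.2 is the only TEAE definition in either document, and it is literally incomplete. The protocol's worsening language can be read as covering only conditions that predate consent, since Protocol 3.6.1 and 3.6.3 use pre-existing for conditions found at screening. An event that arises after consent is already an adverse event, and nothing says that its later worsening opens a new record. If it stayed in the old record and the subject withdrew because of it, disposition could show a discontinuation for an adverse event that the TEAE tables do not contain. With few subjects in each arm, one omitted subject would be a visible share of that arm. One sentence would settle the matter.

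Part of this stands. The text is silent, the reading of pre-existing is arguable, and a clarifying line would do no harm. The rest does not carry the point. The mismatch arises only if the worsening is kept in the pre-dose record, and the action-taken categories in Protocol 3.6.2 make that an awkward fit. The CRF, to which the SAP defers for data collection, was not available, and the mock-up section (SAP 6.3) survives in the reviewed copy as a heading only. A recording rule or table footnote may sit in either, so silence in the available text does not show a gap in the plan. The proposed sentence also gains nothing where worsening is a new record, and little where it is not.

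**Conclusion.** No change is needed. The definition omits a detail that the protocol's recording rules largely supply and that an analyst can handle sensibly. The cases it could miss are confined to events that start between consent and first dose, and only if a later worsening is kept under the old onset date.

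This rests on two points that could not be confirmed. The first is that post-dose worsening is entered as a new adverse event, which Protocol 3.6.2 and 3.6.3 suggest but do not state. The second is that the CRF holds one severity grade per event, as Protocol 3.6.2 describes. If the first holds, the SAP rule already captures the worsening. If it fails and the second holds, a broader definition could seldom be applied. If both fail, so that the CRF tracked severity over time within one record, a descriptive count might omit an event. A reader could still find that event among the records of 13 randomized subjects, and no test or stated conclusion would move.

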5.3 Efficacy

For Psoriasis Area and Severity Index (PASI), Static Physician's Global Assessment (sPGA) and Skindex-16 questionnaire, change from baseline will be derived. In addition, percentage change from baseline will be derived for PASI score and psoriasis affected Body Surface Area (BSA).

Skindex-16 questionnaire is reported in a scale of 0 to 6. Each raw score will be multiplied by 16.667, thus all responses will be transformed to a linear scale of 100 (i.e., from 0 [no effect] to 100 [effect experienced all the time]). Scale scores are the average of non-missing items in a given scale as follows. If any scale has more than 25% of the responses missing, the scale is missing.

- Symptom scale score: average of items 1-4
- Emotions scale score: average of items 5-11
- Functioning scale score: average of items 12-16
- Total score: average of 16 item

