4. Inclusion/Exclusion Criteria Not Met: If a subject who did not meet any of the study inclusion or exclusion criteria is identified after the randomization, the Investigator, Medical Monitor and Sponsor will review that subject profile, including the medical history, prior and current concomitant medications, physical examination, vital signs, 12-lead ECGs and clinical laboratory test results. Since such deviations are usually noted after randomization, the decision to be made is to allow the subject to continue the study or not. For such cases, an exception may be permitted on a case-by-case basis if the subject was randomized into the study due to a minor error determined to be of no clinical and/or safety risk to the subject. Some of the examples where case-by-case basis exceptions may be allowed are as follows:

-
- A subject who had a minor deviation from the inclusion/exclusion criteria defined for the efficacy evaluation purpose (e.g., inclusion criteria 1 through 6, exclusion criteria 1 through 4).
 - A subject who had a minor deviation in clinical laboratory test results from the cut-off values defined in exclusion criteria 6 through 11.
5. Protocol Violation: the subject is non-compliant with regard to this protocol (other than the withdrawal criteria 3 and 4 listed above), as determined by Sponsor or the Investigator on a case-by-case basis.
 6. Lost to Follow-up
 7. Death
 8. Study Terminated by Sponsor: the sponsor may suspend or terminate the study or part of the study at any time for any reason.
 9. Pregnancy
 10. Investigator Decision: the Investigator decides a subject should be discontinued for any reasons other than those already mentioned (actual reason must be documented by site).
 11. Other: actual reason must be documented by site.

Subjects who are removed from the study or withdraw consent to participate in the study after receiving at least one dose of study drug will be requested to complete an Early Termination Visit at which time the subject will undergo all the procedures described for Visit 6. Every effort should be made to perform the Visit 6 assessments as soon as possible after the last dose of study drug and the decision of discontinuation is made and prior to any changes made in the subject's anti-psoriasis therapy. Additionally, at approximately 4 weeks after study drug discontinuation, subject should return for a Follow-up Visit, where all procedures as described at Visit 7 should be performed.

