3.8.1.3 Intent-To-Treat (ITT) Population

The ITT population consists of the randomized subjects who receive at least one dose of the study drug per randomization and have at least one post-randomization efficacy data.

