3.8.3.1 Efficacy Parameters

The primary efficacy parameter is the proportion of subjects achieving PASI 75 at EOT.

[figure not shown]
The secondary efficacy parameters are (evaluated at Weeks 2, 4, 8, 12 and 16, unless otherwise stated):

- Percent change from baseline in PASI score;
- Proportions of subjects achieving PASI 50, PASI 75, PASI 90 and PASI 100;
- Proportion of subjects achieving a sPGA score of 0 or 1;
- Change from baseline in sPGA score;
- Percent change from baseline in the psoriasis affected BSA;
- Change from baseline in Skindex-16;

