3.8.3.2 Efficacy Data Analysis

For the purpose of efficacy analysis, the EOT value is defined as the last value taken during the double-blind treatment period after the first dose of study drug, without any treatment intervention.

Conventional statistical evaluations for efficacy parameters will also be conducted as described below:

For the primary efficacy parameter (PASI 75 at EOT), the Fisher's exact test will be used to compare each JTE-051 dose group with placebo. 

For dichotomous secondary efficacy parameters, similar analyses as the primary efficacy parameter will be used by time point, [REDACTED]

[figure not shown]
[REDACTED]

For continuous efficacy parameter analysis with multiple time points, a mixed effect model will be employed. It includes fixed effects for treatment, time, treatment by time interaction, the stratification factor and the appropriate baseline and subject as the random effect. The appropriate baseline will be the parameter from which the efficacy parameter is derived, e.g., PASI score at Week 0 for the analysis of percent change from baseline in PASI score. The treatment effect of each JTE-051 dose group relative to placebo at the same time point will be estimated. A linear trend test at each time point will be computed using appropriate linear contrast.

All analyses will be performed two-sided at the 5% significance level. No formal multiple comparison adjustment will be made, therefore, results should be interpreted with the multiplicity in mind. The estimated treatment effect (relative to placebo) from the model, along with a two-sided 95% CI and p-value, will be tabulated where appropriate. The Newcombe's CI of the rate difference between JTE-051 dose and placebo will be computed when performing the Fisher's exact test. Graphical presentations of the treatment profile may be depicted. Sensitivity analysis, model fit assessment may be conducted and data transformation may be employed if appropriate.

Descriptive statistics of efficacy parameters over time will be presented by treatment. It will include the number of subjects (N), arithmetic mean, standard deviation (SD), median, minimum and maximum for continuous parameters, and in frequency tabulation form for dichotomous parameters.

[REDACTED]

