2. OBJECTIVES

- To evaluate the efficacy of JTE-051 administered for 12 weeks in subjects with moderate to severe plaque psoriasis.
- To evaluate the safety and tolerability of JTE-051 administered for 12 weeks in subjects with moderate to severe plaque psoriasis.
- To evaluate the pharmacokinetics (PK) of JTE-051 administered for 12 weeks in subjects with moderate to severe plaque psoriasis.

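### Does the SAP need a planned count of the primary endpoint, PASI 75 at end of treatment, now that the trial has stopped at 13 subjects?

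*SAP*

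**What the plan says.** **Protocol.** Section 3.8.3.1 names one primary parameter: "The primary efficacy parameter is the proportion of subjects achieving PASI 75 at EOT". Section 3.8.3.2 takes the EOT value as the last one obtained "during the double-blind treatment period after the first dose of study drug, without any treatment intervention". It plans Fisher's exact test of each dose against placebo, and frequency tables by treatment for dichotomous efficacy parameters. Efficacy analyses use the ITT population, meaning randomized subjects who "receive at least one dose of the study drug per randomization and have at least one post-randomization efficacy data". Section 3.8 allows the SAP to change these plans. It says a major change to the primary analysis may also go into a protocol amendment where appropriate.

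**SAP.** Section 2 keeps the objective: "To evaluate the efficacy of JTE-051 administered for 12 weeks in subjects with moderate to severe plaque psoriasis". Section 4 says the ITT, PP and PK populations "will not be identified in the final analyses due to the early termination of the study and the limited amount of data". Section 5 gives 13 randomized subjects as too few to analyze the planned efficacy and safety endpoints. It drops inferential tests, imputes nothing and sends most data to listings. Section 5.3 contains only the derivations: change from baseline for PASI, sPGA and Skindex-16, and "In addition, percentage change from baseline will be derived for PASI score and psoriasis affected Body Surface Area (BSA"). Table list 6.1 has no efficacy table, and PASI appears in listing 16.2.6.1. For safety, section 5.2 says: "The number and percentage of subjects experiencing TEAEs will be tabulated by treatment in an overall summary".

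**The concern.** The efficacy objective is kept, but the one endpoint meant to answer it has no responder flag, EOT record rule, denominator or table in the visible SAP. Small numbers alone do not seem to explain this, because adverse events are counted by arm in what can be at most the same 13 people.

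Anyone who wants the primary result must build it from listings. Whether a visit reached 75% improvement can be read from the percent change. Which visit is the EOT value must be worked out from PASI dates, dosing (listing 16.2.5.2) and concomitant medication (listing 16.2.4.9). Early-termination assessments add doubt, because protocol section 3.4 asks only that "Every effort should be made to perform the Visit 6 assessments as soon as possible after the last dose of study drug". If two readers chose different records or denominators, they could report different counts for the trial's primary endpoint, and both would have chosen after seeing the data.

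**Working it through.** **1. Size of the trial.** Planned: 5 arms × 17 = 85, which matches the stated total. Randomized: 13. So 13/85 = 15.3%, and 13/5 = 2.6 per arm on average. The actual split is not given; two or three per arm is an assumption based on equal allocation.

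**2. What a test could show.** The smallest possible two-sided Fisher p-value, with all responders in one arm and none in the other:
- 2 vs 2: 2/C(4,2) = 2/6 = 0.33
- 2 vs 3: 1/C(5,2) = 1/10 = 0.10
- 3 vs 3: 2/C(6,3) = 2/20 = 0.10

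No pairwise comparison could reach 0.05, so dropping inference is sound.

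**3. What a descriptive table could show.** With no responders, the exact (Clopper-Pearson) 95% upper limit is 1 − 0.025^(1/n).

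| Responders/n | Exact 95% interval |
|---|---|
| 0/2 | 0 to 84.2% |
| 1/2 | 1.3 to 98.7% |
| 0/3 | 0 to 70.8% |
| 1/3 | 0.8 to 90.6% |

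Pooling all 13 with no responders gives 0 to 24.7%, but that mixes placebo with four doses and describes no treatment.

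**4. Weight of one subject.** One reclassified subject moves an arm's rate by 1/2 = 50 points or 1/3 = 33 points. Leaving out one non-responder turns 1/3 into 1/2. These swings follow from the arm size. A fixed rule would make the count reproducible but no more informative.

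**5. Is the rule really missing?**
- *EOT record.* Protocol 3.8.3.2 defines it as the last value in the treatment period, so an early last value qualifies by definition. Choosing it is not imputation and does not conflict with SAP section 5.
- *Early Termination Visit.* Protocol 3.5.2, the section on the double-blind treatment period, describes this visit and gives it the Visit 6 procedures. Visit 6 itself falls the day after the last dose and closes that period. An assessment shortly after the last dose is therefore not outside it.
- *Denominator.* Protocol 3.8.1.3 defines ITT. A subject with no post-randomization efficacy data is excluded by that definition.
- *What stays undefined.* The phrase about treatment intervention that ends the EOT definition. Protocol Table 2 lists the restricted psoriasis therapies, which is the natural reading. That looseness is in protocol 3.8.3.2, not SAP 5.3.

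**6. Is efficacy treated differently from the rest?** SAP list 6.1 tabulates disposition and treatment-emergent adverse events, lists serious events and events leading to discontinuation, and gives laboratory normal ranges. By list 6.2, demographics, laboratory results, vital signs, ECG and plasma concentrations go to listings only. The PK objective is also retained with no PK table. Efficacy follows the general rule, and adverse events are the exception.

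**7. Reading burden.** At most 13 × 4 = 52 scheduled on-treatment PASI records (Weeks 2, 4, 8 and 12).

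**The case for a change.** The strongest case for a change is that the protocol planned frequency tables for dichotomous efficacy parameters as well as tests, and the SAP drops both. It gives one reason, too few data for efficacy and safety alike, and then tabulates adverse events by arm without saying why a count suits one and not the other. The remedy is cheap: a flag and a short table over at most 52 records, with the EOT rule and denominator stated. Because the study was stopped early, some EOT values may precede Week 12, which makes choosing the record a practical matter.

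Part of this stands. The visible SAP does not mention PASI 75, the contrast with adverse events is not explained, and the protocol leaves treatment intervention undefined. SAP section 1 refers to the protocol for conduct and data collection and does not explicitly carry the EOT rule over.

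It does not amount to a defect. An adverse-event count means something at any length of exposure. A 12-week response rate under truncated exposure means much less. The EOT and ITT definitions were fixed in the protocol, so a reader who applies them is not inventing rules after seeing the data. No document shows a subject whose EOT record is in dispute. A table of rates on two or three subjects also carries a cost, because it invites over-reading.

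**Conclusion.** No change follows. Listing rather than tabulating the primary endpoint is a disclosed and fair trade-off in a trial that stopped at 15.3% of its planned size. Followed as written, the SAP reaches no efficacy conclusion, so the omission cannot produce a wrong one. The derivation of PASI percent change and the PASI listing are kept. A PASI 75 table would carry upper limits of 70.8% to 84.2% at zero responders and would leave what the trial can conclude unchanged.

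This rests on two or three subjects per arm (the split is not stated) and on the visible SAP text. The mockups in section 6.3 are not shown and might contain a responder column. The number of dosed subjects is also not stated and is at most 13.

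A sponsor could add one line of responders over subjects assessed per arm, using the protocol's EOT and ITT definitions, or one sentence saying that PASI 75 at EOT will not be summarized. Either would be a convenience to readers.
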